6.2 Other Safety Endpoints

- Visual acuity
- Slit-lamp evaluation
- Adverse event query
- Intraocular Pressure (IOP)
- Dilated fundoscopy
- Central Cornea Endothelial Cell Counts (1-year LTFU subjects only)
- Blood chemistry and hematology analysis in a subset of subjects (1-year LTFU subjects only)
- Unanesthetized Schirmer's Test

6.3 Other Measures

- Urine Pregnancy Test

7 STUDY MATERIALS

7.1 Study Drug(s)

7.1.1 Study Drug(s)/ Formulation(s)

- 0.25% Reproxalap Ophthalmic Solution (reproxalap)

- Vehicle Ophthalmic Solution (vehicle)

7.1.2 Study Drug Packaging Configuration

Study drug and vehicle vials are packaged in 5 count pouches, which will then be packaged into kits that will supply for 2-week periods. These kits will be made of 14 of the 5 count pouches.

7.1.3 Study Drug Storage and Accountability

The study drug must be stored in a secure area accessible only to the investigator and his/her designees. The study drug will be administered only to subjects entered into the clinical study, in accordance with the conditions specified in this protocol.

The study drug is to only be prescribed by the principal investigator or his/her named sub investigator(s), and is to only be used in accordance with this protocol. The study drug must only be distributed to subjects properly qualified under this protocol to receive study drug. The investigator must keep an accurate accounting of the study drug by maintaining a detailed inventory. This includes the amount of study drug received by the site, amount dispensed to subjects, amount returned to the site by the subjects, and the amount returned to the Sponsor upon the completion of the study.

7.1.4 Instructions for Dispensation, Use, and Administration

- The vehicle solution consists of all components of the drug product solution with the exception of reproxalap.
- At the study site, all Investigational Product (IP) must be stored under the conditions specified in the Investigator's Brochure in a secure area accessible only to the designated qualified clinical site personnel. All IP must be stored, inventoried and the inventories carefully and accurately documented according to applicable state, federal and local regulations, International Council on Harmonisation (ICH) Good Clinical Practices (GCPs) and study procedures.

- Subjects will receive 3 treatment kits or 14 treatment kits (Long-Term Follow-up Group). After Visit 2 all subjects will change their dosing regimen from QID to BID for the remainder of the treatment period.
- At a minimum, the immediate or secondary study drug packaging will provide the following information: study Sponsor identification, directions for use, required storage conditions, caution statements (including “New Drug—Limited by Federal Law to Investigational Use” language), and study identification.

7.2 Other Study Supplies

Other study supplies include urine pregnancy tests, Schirmer’s test strips, sodium fluorescein, Fluress, and Tropicamide.

8 STUDY METHODS AND PROCEDURES

8.1 Subject Entry Procedures

8.1.1 Overview

Subjects as defined by the criteria in Sections 5.2, 5.3, and 5.4 will be considered for entry into this study.

8.1.2 Informed Consent

Prior to a subject’s participation in the trial (i.e., prior to changes in a subject’s medical treatment and/or prior to study related procedures), the study will be discussed with each subject, and subjects wishing to participate must give written informed consent using an informed consent form (ICF). The informed consent form must be the most recent version that has received approval/favorable review by a properly constituted Institutional Review Board (IRB).

8.1.3 Washout Intervals

Prohibited medications, treatments, and activities are outlined in the Exclusion Criteria (Section 5.4).

8.1.4 Procedures for Final Study Entry

Subjects must meet all inclusion and none of the exclusion criteria.

8.1.5 Methods for Assignment to Treatment Groups:

Prior to randomization (at Visit 1), each subject who signs the informed consent will be assigned a screening number. All screening numbers will be assigned in strict numerical sequence at each site and no numbers will be skipped or omitted.

At Visit 1, a patient who meets all the eligibility criteria will be randomized to receive treatment 0.25% Reproxalap Ophthalmic Solution or placebo in a 2:1 ratio by the IWRS.

The Interactive Web Response System (IWRS) will assign the randomization number and the assigned kit number for the patient. The site staff will dispense to the patient the study kit labeled with the corresponding kit number. Randomization will be stratified by follow-up schedule (6-week follow-up vs 1-year follow-up). Both the randomization number and the dispensed study drug kit number will be recorded on the patient's source document and eCRF.

8.2 Concurrent Therapies

The use of any concurrent medication, prescription or over-the-counter, is to be recorded on the subject's source document and corresponding electronic case report form (eCRF) along with the reason the medication was taken.

Concurrent enrollment in another investigational drug or device study is not permitted.

8.2.1 Prohibited Medications/Treatments

Disallowed medications/treatments during the study are outlined in the Exclusion Criteria (Section 5.4).

8.2.2 Escape Medications

No escape medications are required for this study.

8.2.3 Special Diet or Activities

No special diets or activities are required for this study.

8.3 Examination Procedures

[figure not shown]
[figure not shown]
8.3.1 Procedures to be Performed at Each Study Visit with Regard to Study Objective(s)

The following procedures will be performed (see Appendix 2 for description):

Visit 1 (Day 1): Screening & Randomization

[figure not shown]
- Informed consent / Health Information Portability and Accountability Act (HIPAA);

[figure not shown]

- Qualified subjects will be scheduled for Visit 2.

[figure not shown]
[figure not shown]
Visit 2 (Day 29 ±3 days): 4-Week Follow-up

- Schedule subjects for Visit 3.

[figure not shown]
Visit 3 (Day 43 ± 4 days): 6-Week Follow-Up

- Schedule subjects for Visit 4.

[figure not shown]
Visit 4 (Day 90 ± 7 days): 3-Month Follow-up

Long-Term Follow-up (LTFU) Subjects Only

Visit 5 (Day 180 ± 7 days): 6-Month Follow-up

Long-Term Follow-up (LTFU) Subjects Only

[figure not shown]

Schedule subjects for Visit 6.

Visit 6 (Day 270 ± 10 days): 9-Month Follow-up

[figure not shown]
Long-Term Follow-up (LTFU) Subjects Only

[figure not shown]

- Schedule subjects for Visit 7.

Visit 7 (Day 360 ± 10 days): 1-Year Follow-up

Long-Term Follow-up (LTFU) Subjects Only

- Study Exit

Early Termination/Discontinuation

If a subject is discontinued from the study prior to Visit 7 (Day 360 ± 10), then all safety evaluations that are to be performed at Visit 7 should be performed on the day of discontinuation (early termination) or at the discretion of the investigator.

Adverse Events (both elicited and observed) and SAEs will be monitored throughout the study. The investigator will promptly review all adverse events (both elicited and observed) for accuracy and completeness. All adverse events will be documented on the appropriate source document and eCRF. If a female reports a pregnancy or has a positive pregnancy test during the study, then the investigator will notify [REDACTED] immediately. The investigator shall instruct the patient to immediately stop the study medication and request from the subject and/or the subject's physician copies of all related medical reports during the pregnancy and shall document the outcome of the pregnancy. The investigator will retain these reports together with the subject's source documents and will provide a copy of all documentation to [REDACTED]

8.4 Schedule of Visits, Measurements and Dosing

[figure not shown]
8.4.1 Scheduled Visits

Refer to Appendix 1 for a schedule of visits and measurements.

8.4.2 Unscheduled Visits

These visits may be performed in order to ensure subject safety. All procedures performed at an unscheduled visit will be recorded in the source documents and on the Unscheduled Visit eCRF pages. Any procedure indicated in the eCRF that is not performed should be indicated as "Not done."

Evaluations that may be conducted at an Unscheduled Visit include:

8.5 Compliance with Protocol

Subjects will be instructed on proper instillation and storage of study drug at the end of each visit (except the subject's final visit) and given written instructions. The subject's used and unused study drug ampules will be collected at each visit from Visit 2 up to and including Visit 3 or Visit 7 (Long-Term Follow-up subjects) to assess dosing compliance. Dosing compliance will be based on the unused ampule count. If the subject is less than 80% or more than 125% compliant with dosing based on the expected number of unused ampules, then the subject will be deemed non-compliant and a dosing deviation should be recorded.

These guidelines will be used by the Investigator for determining the subject's necessary compliance for the study and for recording deviations from this compliance.

8.6 Subject Disposition

8.6.1 Completed Subjects

A completed subject is one who has not been discontinued from the study.

8.6.2 Discontinued Subjects

Subjects may be discontinued prior to their completion of the study due to:

- adverse events;
- protocol violations;
- administrative reasons (e.g., inability to continue due to scheduling changes);
- lost to follow up;
- sponsor termination of study;
- subject choice (e.g. withdrawal of consent); and
- other

Note: In addition, any subject may be discontinued for any sound medical reason at the discretion of the investigator.

Discontinuations that are the direct result of SARS-CoV-2 (COVID-19) will be classified separately and clearly documented in the eCRF. A separate field will be completed to denote a COVID-19 related discontinuation and the specific reason will be documented utilizing the above noted list of subcategories.

Notification of a subject discontinuation and the reason for discontinuation will be made to [REDACTED] study sponsor and will be clearly documented on the eCRF.

8.7 Study Termination

The study may be stopped at any time by the investigator, the sponsor, [REDACTED] with appropriate notification.

8.8 Study Duration

An individual subject's participation will involve either 3 visits over approximately a 6-week period (42 days) or 7 visits over approximately a year (360 days).

8.9 Monitoring and Quality Assurance

During the course of the study a monitor, or designee, will make routine site visits to review protocol compliance, assess study drug accountability and storage conditions, subject safety, and ensure the study is being conducted according to the pertinent regulatory requirements. The review of the subjects' medical records will be performed in a manner that adequately maintains subject confidentiality. Further details of the study monitoring will be outlined in a monitoring plan.

Regulatory authorities of domestic and foreign agencies, [REDACTED] quality assurance, the sponsor and/or its designees may carry out on-site inspections and/or audits, which may include source data checks. Therefore, direct access to the original source data will be required for inspections and/or audits. All inspections and audits will be carried out giving consideration to data protection as well as subject confidentiality to the extent that local, state, and federal laws apply.

9 ADVERSE EVENTS

9.1 Adverse Event

An adverse event is defined as any untoward medical occurrence associated with the use of a drug in humans, whether or not the event is considered IP-related. An adverse event can therefore be any unfavorable and unintended sign (e.g., an abnormal laboratory finding), symptom, or disease occurring after the subject started dosing with the IP,

without any judgment about causality. An AE can arise from any use of the IP (e.g., off-label use, use in combination with another drug or medical device) and from any route of administration, formulation, or dose, including an overdose. An AE can arise from any delivery, implantation, or use of a medical device, including medical device failure, subject characteristics that may impact medical device performance (e.g., anatomical limitations), and therapeutic parameters (e.g., energy applied, sizing, dose release, and anatomic fit) associated with medical device use.

All AEs spontaneously reported by the subject and/or in response to an open question from study personnel or revealed by observation, physical examination or other diagnostic procedures will be recorded in the source document and on the appropriate pages of the CRF. Any clinically relevant deterioration in clinical finding is considered an AE and must be recorded. When possible, signs and symptoms indicating a common underlying pathology should be noted as one comprehensive event.

Any pre-existing medical condition that worsens after administration of the IP will also be considered a new adverse event.

[figure not shown]
If there is a worsening of a medical condition that was present prior to the administration of the IP, this should also be considered a new adverse event and reported. Any medical condition present prior to the administration of the IP that remains unchanged or improved should not be recorded as a treatment emergent adverse event at subsequent visits unless it worsens during treatment.

[figure not shown]
Investigational Product (IP) includes the investigational drug under evaluation and placebo, or any other medications required by the protocol given during any stage of the study.

Documentation regarding the adverse event should be made as to the nature, date of onset, end date, severity, relationship to IP, action(s) taken, seriousness, and outcome of any sign or symptom observed by the physician or reported by the patient upon indirect questioning.

9.1.1 Severity

Severity of an adverse event is defined as a qualitative assessment of the degree of intensity of an adverse event as determined by the investigator or reported to him/her by the patient/subject. The assessment of severity is made irrespective of relationship to IP or seriousness of the event and should be evaluated according to the following scale:

9.1.2 Relationship to Investigational Product

The relationship of each adverse event to the Investigational Product (IP) should be determined by the investigator using these explanations:

- *Definite*: When there are good reason and sufficient documentation to demonstrate a direct causal relationship between investigational product and AE;
- *Probable*: When there are good reasons and sufficient documentation to assume a causal relationship in the sense of plausible, conceivable, likely but not necessarily highly probable.
- *Possible*: When there is sufficient information to accept the possibility of a causal relationship in the sense of not impossible and not unlikely, although the connection is uncertain or doubtful, for example, due to missing data or insufficient evidence.
None: When there is sufficient information to accept a lack of a causal relationship, in the sense of impossible and improbable.
- *Unclassified*: When the causal relationship is not assessable for whatever reason due to insufficient evidence, conflicting data or poor documentation.

Suspected adverse reaction means any adverse event for which there is a reasonable possibility that the IP caused the adverse event. “Reasonable possibility” means there is evidence to suggest a causal relationship between the IP and the adverse event. Types of evidence that would suggest a causal relationship between the IP and the adverse event include: a single occurrence of an event that is uncommon and known to be strongly associated with drug exposure (e.g., angioedema, hepatic injury, Stevens-Johnson Syndrome); one or more occurrences of an event that is not commonly associated with drug exposure, but is otherwise uncommon in the population exposed to the drug (e.g., tendon rupture); an aggregate analysis of specific events observed in a clinical trial (such as known consequences of the underlying disease or condition under investigation or other events that commonly occur in the study population independent of drug therapy) that indicates those events occur more frequently in the drug treatment group than in a concurrent or historical control group.

9.1.3 Expectedness

The expectedness of an adverse event should be determined based upon existing safety information about the IP using these explanations:

- *Unexpected*: An adverse event that is not listed in the Investigator's brochure or is not listed at the specificity or severity that has been observed.
- *Expected*: An adverse event that is listed in the Investigator's brochure at the specificity and severity that has been observed.
- *Not Applicable*: Any adverse event that is unrelated to the IP.

Adverse events that are mentioned in the Investigator's brochure as occurring with a class of drugs or as anticipated from the pharmacological properties of the drug but are not specifically mentioned as occurring with the particular drug under investigation are to be considered unexpected.

The investigator should initially classify the expectedness of an adverse event, but the final classification is subject to the Medical Monitor's determination.

9.2 Serious Adverse Events

An adverse event is considered serious if, in the view of either the investigator or sponsor, it results in any of the following outcomes:

- Death;
- A life-threatening adverse event;

Note: An adverse event is considered "life-threatening" if, in the view of either the investigator or sponsor, its occurrence places the patient or subject at immediate risk of death. It does not include an adverse event that, had it occurred in a more severe form, might have caused death.

- Inpatient hospitalization or prolongation of existing hospitalization;

Note: The term "inpatient hospitalization" refers to any inpatient admission (even if less than 24 hours). For chronic or long-term inpatients, inpatient admission includes transfer within the hospital to an acute/intensive care inpatient unit. Inpatient hospitalization does not include: emergency room visits; outpatient/same-day/ambulatory procedures; observation/short stay units; rehabilitation facilities; hospice facilities; nursing homes; or clinical research/phase 1 units.

Note: The term "prolongation of existing hospitalization" refers to any extension of an inpatient hospitalization beyond the stay anticipated or required for the reason for the initial admission as determined by the investigator or treating physician.

- A persistent or significant incapacity or substantial disruption of the ability to conduct normal life functions;

Note: A serious adverse event specifically related to visual threat would be interpreted as any potential impairment or damage to the subject's eyes (e.g., hemorrhage, retinal detachment, central corneal ulcer or damage to the optic nerve).

- A congenital anomaly/birth defect.

Important medical events that may not result in death, are life-threatening, or require hospitalization may be considered serious when, based upon appropriate medical judgment, they may jeopardize the patient or subject and may require medical or surgical intervention to prevent one of the outcomes listed in this definition.

9.3 Procedures for Reporting Adverse Events

All adverse events and their outcomes must be reported to [REDACTED] the study sponsor, and the IRB as required by the IRB, federal, state, or local regulations and governing health authorities and recorded on the appropriate eCRF.

9.3.1 Reporting a Suspected Unexpected Adverse Reaction

All adverse events that are 'suspected' and 'unexpected' are to be reported to [REDACTED] the study sponsor and the IRB as required by the IRB, federal, state, or local regulations and governing health authorities.

9.3.2 Reporting a Serious Adverse Event

To ensure subject safety, all serious adverse events, regardless of relationship to the study drug, must be immediately reported. All information relevant to the serious adverse event must be recorded on the appropriate eCRF. The investigator is obligated to pursue and obtain information requested by [REDACTED] and/or the sponsor in addition to that information reported on the eCRF. All subjects experiencing a serious adverse event must be followed up and the outcome reported.

In the event of a serious adverse event, the investigator must notify [REDACTED] and the sponsor immediately (within 24 hours); obtain and maintain in his/her files all pertinent medical records, information, and medical judgments from colleagues who assisted in the treatment and follow-up of the subject; provide [REDACTED] the study sponsor with a complete case history, which includes a statement as to whether the event was or was not suspected to be related to the use of the study drug; and inform the IRB of the adverse event within their guidelines for reporting serious adverse events.

Serious adverse events should be reported within one day to the contacts listed below:

Name

Title:

Company:

Mobile Phone:

Email:

Name

Title:

Office Telephone:

Mobile Phone:

Office Facsimile:

9.4 Procedures for Unmasking of Study Drug

All subjects, investigators, and study personnel involved with the conduct of the study will be masked with regard to treatment assignments. When medically necessary, the investigator may need to determine what treatment arm has been assigned to a subject. When possible (i.e., in non-emergent situations), [REDACTED] and/or the study sponsor should be notified before unmasking study drug as described in the following paragraph.

If an investigator identifies a medical need for unmasking the treatment assignment of a subject, he/she should contact [REDACTED] and/or the medical monitor prior to unmasking the identity of the IP, if possible. [REDACTED] will ask the site to complete and send them the Unmasking Request Form. [REDACTED] will notify Aldeyra and jointly will determine if the unmasking request should be granted. They may consult the medical monitor as needed. The result of the request will be documented on the Unmasking Request Form. If approval is granted to unmask a subject, written permission via the Unmasking Request Form will be provided to the investigator. The investigator will unmask the subject using IWRS. The investigator will complete the Unmasking Memo form and include it in the subject's study file and provide a copy for the Trial Master File (TMF). For each unmasked request, the reason, date, signature, and name of the person who unmasked the subject, must be noted in the subject's study file.

9.5 Type and Duration of the Follow-up of Subjects after Adverse Events

Adverse events that are ongoing at the end of the study visit will be followed. Phone calls will be placed with any subject who experiences an adverse event until the issue is resolved or the condition is considered ongoing and stable.

10 STATISTICAL HYPOTHESES AND METHODS OF ANALYSES

10.1 Analysis Populations

Safety Population – The safety population will include all subjects receiving treatment from whom at least one safety measurement is obtained following the first dose of study drug. The safety population will be analyzed for all safety assessments.

Safety-LTFU Population – The Safety population will include all LTFU subjects receiving treatment from whom at least one safety measurement is obtained following the first dose of study drug. The Safety-LTFU population will be analyzed for all safety assessments. Subjects in the Safety-LTFU population will be analyzed as treated. Subjects in the Safety population will be analyzed as treated.

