	
• Visit 1 = Screening & Randomization• Visit 2 = Day 29 ± 3, 4-Week Follow-Up• Visit 3 = Day 43 ± 4, 6-Week Follow-Up (Exit for approximately 300 subjects)• Visit 4 = Day 90 ± 7, 3-Month follow-up• Visit 5 = Day 180 ± 7, 6-Month follow-up• Visit 6 = Day 270 ± 10, 9-Month follow-up• Visit 7 = Day 360 ± 10, 1-Year follow-up & Exit
Measures Taken to Reduce Bias:	Randomized treatment assignment, double-masked trial
Study Population Characteristics	
Number of Subjects:	Approximately 1050 subjects are expected to be screened to enroll 850 subjects into the trial. Approximately 550 subjects will continue after Week 6 for the Long-Term Follow-up portion, with the goal of approximately at least 100 reproxalap subjects completing at 1 year.
Condition/Disease:	Dry Eye Disease (DED)

Inclusion Criteria:	Subjects must meet all of the following criteria: 
1. At least 18 years of age (either gender and any race);2. Ability to provide written informed consent and sign the Health Information Portability and Accountability Act (HIPAA) form;3. Reported history of dry eye for at least 6 months prior to Visit 1;4. History of use or desire to use eye drops for dry eye symptoms within 6 months of Visit 1; 
Exclusion Criteria:	Subjects must not meet any of the following criteria: 
1. Clinically significant slit lamp findings at Visit 1 that may include active blepharitis, meibomian gland dysfunction (MGD), lid margin inflammation, or active ocular allergies that require therapeutic treatment, and/or in the opinion of the investigator may interfere with study parameters;2. Diagnosis of an ongoing ocular infection (bacterial, viral, or fungal), or active ocular inflammation at Visit 1;3. Contact lens use within 7 days of Visit 1 or anticipate using contact lenses during the trial;4. Eye drop use within 2 hours of Visit 1;

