4 OVERALL STUDY DESIGN

The ADX-102-DED-021 clinical trial is a Phase 3, multicenter, randomized, double-masked, parallel-group, vehicle-controlled design. Subjects will be randomized to one of the following treatment groups at Visit 2:

[figure not shown]
- 0.25% Reproxalap Ophthalmic Solution (reproxalap)
- Vehicle Ophthalmic Solution (vehicle)

[figure not shown]
Approximately 850 subjects will be randomly assigned to one of the two treatment groups (2:1) to receive either reproxalap or vehicle as topical ophthalmic drops administered bilaterally QID for four weeks followed by BID dosing for weeks 5-6. Approximately 550 subjects will dose QID for four weeks and continue dosing BID for the following 11 months. Subjects, Sponsor, CRO, and site personnel will be masked to treatment assignment.

All subjects will dose with randomized treatment QID between Visit 1 and Visit 2 and switch to BID dosing between Visit 2 and Visit 4 or between Visits 2 and Visit 7 for the long-term follow-up group.

The total number of expected participants, including screen failures, is approximately 1050 subjects.

A study flow chart appears below:

Subjects who terminate early during the treatment period will be asked to complete safety assessments prior to commencement of alternative DED therapy (if possible). [REDACTED]

[REDACTED]

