10.4 Statistical Analysis

10.4.1 General Considerations

Quantitative variables will be summarized using number of subjects (n), mean, median, standard deviation, minimum and maximum. The dichotomous variables will be summarized using counts and percentages.

Summaries will be provided for demographics, baseline medical history, concurrent therapies, and subject disposition.

Baseline measures are defined as the last measure prior to the administration of study treatment at Visit 1 (Day 1). Change from baseline will be calculated as Visit – Baseline.

For the purpose of summarization, medical history, concurrent therapies, and AEs will be coded to MedDRA and WHO Drug dictionaries, as appropriate.

[figure not shown]
[figure not shown]
[figure not shown]

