10.4.6 Other Safety Analyses

Dosing information will be summarized overall subjects and listed for each subject will be listed. Discontinuation of treatment will be summarized by treatment received. The primary reason for trial drug discontinuation will also be summarized by treatment received.

Adverse events (AEs) will be coded using the MedDRA dictionary. An AE is treatment emergent if it occurs or worsens after the first dose of study treatment.

Frequencies and percentages of subjects with treatment-emergent adverse events (TEAEs), serious TEAEs, and TEAEs causing premature treatment discontinuation will be provided by treatment group. Furthermore, frequencies will be given of subjects with TEAEs by system organ class and preferred term for the following categories of AEs:

- All TEAEs
- TEAEs at least possibly related to study treatment
- TEAEs leading to study treatment discontinuation
- Serious TEAEs
- By maximal severity
- By study day of onset

Separate analyses will be performed for ocular and non-ocular AEs. Separate analyses of AEs will be generated for the Safety population with 6 weeks of follow-up and the Safety-LTFU population with 6 months of follow-up (or 1 year of follow-up).

Other safety endpoints will be summarized by treatment group and visit using descriptive statistics. Changes or shifts from baseline will also be summarized where appropriate. Separate analyses will be generated for the Safety population with 6 weeks of follow-up and the Safety-LTFU population with 6 months of follow-up (or 1 year of follow-up).

Assessments performed by eye will be summarized separately for right eye and left eye.

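### Treated subjects who leave before Day 29 with no recorded contact fall outside both safety populations

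*Combined protocol and SAP*

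**What the plan says.** The Synopsis and Section 10.1 define the Safety population as "all subjects receiving treatment from whom at least one safety measurement is obtained following the first dose of study drug", analysed as treated. Safety-LTFU is "all LTFU subjects receiving treatment from whom at least one safety measurement is obtained following the first dose of study drug". Section 10.1 adds: "The safety population will be analyzed for all safety assessments". The readable text does not define what counts as a safety measurement.

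Section 10.4.1 places the first administration of study treatment at Visit 1 (Day 1). The Synopsis then lists "Visit 2 = Day 29 ± 3, 4-Week Follow-Up" as the next visit, and Section 8.3.1 and Appendix 1 agree.

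Four provisions can produce an earlier observation:

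- Section 8.3.1 says the Visit 7 safety evaluations "should be performed on the day of discontinuation (early termination) or at the discretion of the investigator" for a subject who discontinues before Visit 7.
- Section 4 has early leavers asked to complete safety assessments where this is possible.
- Section 8.4.2 permits unscheduled visits.
- Section 9.1 has spontaneously reported adverse events recorded, and Section 6.2 lists the adverse event query as a safety endpoint.

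Under Other Safety Analyses, Section 10.4.6 says: "Discontinuation of treatment will be summarized by treatment received". It plans the same for the primary reason, and names no population for either summary.

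**The concern.** Membership of both populations depends on something that happens after treatment starts. A rule of that kind can select differently in the two arms if one treatment leads more subjects to stop coming. The only stated objective of this trial is to compare safety, so every treated subject should be accounted for in the safety comparison.

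The timing makes this more than a formality, because there are about four weeks of dosing before the next listed visit. Section 8.6.2 foresees loss to follow-up and withdrawal by choice. A subject who takes the drug and is not heard from again is treated, but drops out of the TEAE denominators. If the discontinuation summaries use the same population, that subject's stopping is not counted either. The readable text does not ask for the number of such exclusions by arm, so a difference between arms could go unseen.

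**Working it through.** The plan states no figure for treated subjects without a post-dose measurement, and no dropout rate is readable. There is therefore nothing to reproduce, and the loss rates below are assumptions shown over a range.

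**Length of the gap.** Visit 2 falls on Day 29 ± 3, that is Day 26 to Day 32. Counted from the first dose on Day 1, this is 26 − 1 = 25 to 32 − 1 = 31 days without a listed visit.

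**Who is certainly excluded.** Taking the provisions in turn:

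| Subject stops before Day 29 and… | Post-dose safety measurement? |
|---|---|
| attends an early-termination or unscheduled examination | Yes |
| reports an adverse event without attending | Probably; the term is undefined |
| has no visit, no examination and no report | No (unless a post-dose check was done on Day 1) |

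The early-termination examination is left to investigator discretion, the Section 4 request applies only where possible, and unscheduled visits are optional. The third row can therefore occur.

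**Arm sizes.** About 850 subjects are randomised 2:1 (Sections 4 and 5.1): 850 × 2/3 ≈ 567 reproxalap and 850 − 567 = 283 vehicle.

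**Subjects lost, under assumed rates.**

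- 1% in each arm: 0.01 × 567 ≈ 6 and 0.01 × 283 ≈ 3.
- 5% against 2%: 0.05 × 567 ≈ 28 and 0.02 × 283 ≈ 6.

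**What this could do to a TEAE percentage.** Assume, for illustration only, that 10% of the retained reproxalap subjects have a TEAE. With *x* of 567 excluded, the retained number is *n* = 567 − *x*. Two extremes bound the all-treated percentage: no excluded subject had an event, 0.10*n*/567, or every one did, (0.10*n* + *x*)/567.

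| Excluded *x* | *n* | None had an event | All had an event |
|---|---|---|---|
| 6 (1%) | 561 | 56.1/567 = 9.9% | 62.1/567 = 11.0% |
| 28 (5%) | 539 | 53.9/567 = 9.5% | 81.9/567 = 14.4% |

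The last column is an upper bound, not an estimate. Each 1% excluded can hide at most about one percentage point of risk.

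**Effect on the primary endpoints.** Under Estimand 1 (Section 10.4.5), subjects who leave the study before the time point without the event of interest are not analysed. Silent early leavers are removed by that rule whichever population definition is used.

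**The case against.** The strongest reply is that the group is small and the change recovers no events. A subject who stops because of discomfort and says so has a recorded adverse event, which on a natural reading is a safety measurement. The subjects certain to be lost are those who left without saying anything, and their experience is unrecorded whatever the denominator. Adding them lowers the TEAE percentages slightly and reveals no hidden harm. The Visit 1 procedures are withheld; if they include a check after dosing, nearly every treated subject already qualifies. The protocol also says that the SAP prevails on statistical language, and no separate SAP definition of the populations could be read for this check.

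Most of this stands, and it sets the limits of the point. It does not remove it: the written rule still selects on a post-treatment event, its key term is undefined, and nothing readable requires the exclusions to be shown by arm.

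A reader might infer two stronger things, and the documents support neither:

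- **That the earliest intolerant dropouts vanish from every safety table.** Reported intolerance is captured under Section 9.1. Neither the discontinuation summaries in Section 10.4.6 nor the disposition summary in Section 10.4.1 is tied to the Safety population. Their denominator is unspecified, not known to be restricted.
- **That the primary comparisons are distorted by this definition.** The estimand excludes silent leavers separately.

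**Conclusion.** The point holds in a limited form. Both safety populations omit treated subjects who leave before Day 29 with no visit, no early-termination examination and no adverse event report. Those subjects are missing from Safety-population tables, and from the discontinuation summaries if these are run on that population.

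The size is unknown. It ranges from negligible (about 6 and 3 subjects at an assumed 1% in each arm) to enough to matter for an early-tolerability comparison (about 28 and 6 at an assumed 5% against 2%). The difference between arms in the second case is chosen for illustration and is not derived from the documents. The conclusion also assumes that no routine post-dose check takes place on Day 1, which can be neither confirmed nor excluded. The change is worth making mainly because it is cheap and gives a complete account of treated subjects by arm.

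**What to change.** In the Synopsis, Section 10.1 and the SAP:

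- Define the Safety population as all subjects who received at least one dose of study drug, analysed as treated.
- Define Safety-LTFU as all such subjects in the 1-year randomisation stratum. Section 8.1.5 already stratifies by follow-up schedule, so this can be applied directly. It also settles whether LTFU subjects are those assigned at Visit 1 or those who continue after Week 6.
- Name these populations as the denominators for the TEAE tables and for the treatment-discontinuation summaries in Section 10.4.6.
- Report, by arm, the number of treated subjects with no post-dose measurement.
- Keep the measurement condition only for tables of change from baseline.

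No new data are needed. The cost is that the added subjects have no recorded events, so TEAE percentages fall slightly: in the illustration, from 10% to 9.9% at 1% excluded and to 9.5% at 5%. The number without follow-up must therefore stand beside those percentages. The change does not return silent leavers to the primary endpoint analyses; that would need a change to the estimand's handling of study discontinuation, which is a separate matter.
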